#### 4. Subject Selection

Recruitment for potential open pilot participants (i.e., RHC patients) will be facilitated through 1) IRB approved flyers, 2) RHC provider referrals, and 3) in-clinic approaches made by study staff (see bullet points below).

1. IRB Approved Flyers: Patients who find the flyer will be able to indicate their interest and provide their contact information by accessing the REDCap link provided on the flyer. Study staff will then follow up over the phone with the patients to discuss the study in more detail and schedule an in-person screening visit. Alternatively, patients may have the option to complete screening over the phone with the RA.
2. IRB Approved Rally Post: Patients who find our study via Rally will be able to indicate their interest on the platform. An RA will follow up with all inquiries over the phone. Once contact has been made, the RA will discuss the study with interested participants and either schedule an in-person screening visit or conduct screening virtually over the phone.
3. RHC Provider Referrals: Patients who receive referrals for the study from their provider or medical interpreter will either self-screen via the link provided on the flyer, be guided through screening at RHC by study staff or be contacted directly via phone call by study staff. Only patients who give their medical provider verbal consent to be called by study staff will be contacted. It will be clearly communicated to medical providers at RHC that they should confirm with their patients that they would like to be contacted by study staff prior to giving referrals. In all cases a baseline in person visit will be conducted with those participants who screen in.
4. In-Clinic Approaches by Study Staff: An RA will facilitate patient recruitment via in-clinic approaches. These approaches will ideally be informed through precursory eligibility assessments made by the RA based on the patient's medical record. If time restrictions do not allow for precursory eligibility assessments, the RA will consult RHC staff regarding their patient recommendations. The trained RA will then approach the patient and ask if they can introduce the study and answer any related questions. If patients indicate they are interested in participating, they will be guided through eligibility screening with the RA in person at RHC, or later on over the phone if the participant expresses interest but cannot be screened at that time. A baseline visit will be conducted in person.

At the conclusion of all screenings, the RA will gather patient availability for the in-person baseline assessment and the 10-week *GetActive+* program and email, mail or hand a copy of the informed consent form to participants. This will allow potential participants ample time to review the consent form prior to the baseline visit. All patients will be instructed not to sign it until they undergo formal consent at the in person visit. The recruitment strategies described above are informed by recommendations from RHC staff and are supported by [REDACTED]. Patients who choose to provide their consent will do so electronically (i.e., eConsent) in the presence of the research assistant to ensure that all questions or concerns associated with participation are answered. Consent will be collected via REDCap, a validated password-protected signature platform approved by MGB. They will receive a signed paper or digital copy of the informed consent form. All participants will be notified that their participation in the following open pilot is voluntary and that they are able to withdraw at any time. All study

participants who are deemed not eligible after screening will be offered a chronic pain resource sheet to provide them with additional pain management resources (email or paper copy). Recruitment procedures for Spanish speaking patients will be identical. All screening for Spanish-speaking patients will be completed with a native Spanish speaking RA. The described methodology has been used successfully by [name] in other behavioral health studies (P#: 2021P002811; P#: 2020P000095). Per MGB policies on email communication, we will be using secure email to communicate with participants. This will be done using the “SEND SECURE” encryption function. To further protect participants’ confidentiality, we will discourage participants from communicating with study staff by non-secure email.

After all group sessions and study assessments have finished, we will create a recruitment video that contains clips of participants speaking briefly to their experience in our groups. Submitting video clips for this recruitment project will be entirely optional, and participants will be informed that the final video will be included in promotional materials for the study. The names or any identifying information for the participants in the video will not be released. All participants will be given the opportunity to contribute a clip to the recruitment video. Participants will be shown their contribution to the video and required to provide written permission by email or paper for the video to be used for recruitment purposes, as described above. We have used this methodology successfully in prior studies (Protocol #2017P000143 and #2022P001766) for creation of a recruitment video, and we found it to work very well with no issue. Participants will also be given the option to submit a group photo for recruitment purposes. All individuals in the photo will also sign the photo release consent form.

**Inclusion Criteria:**

1. Older Adults (i.e., age  $\geq 55$ , since aging is accelerated by impoverished lifestyles)
2. Has diagnosed musculoskeletal chronic pain of any type (e.g., pain duration  $> 3$  months)
3. Pain score  $\geq 4$  (moderate) on the Numerical Rating Scale
4. Cognitively able to participate as measured by the Short Portable Mental Health questionnaires (e.g.,  $< 4$  errors)
5. No self-reported current active, untreated psychotic or substance use disorder that would interfere with participation in the research study
6. Self-reported ability to complete the 6-minute walk test
7. Patient at RHC who is cleared for participation by medical staff
8. English or Spanish fluency.

**Exclusion Criteria:**

1. Current serious medical illness that is expected to worsen in the next 6 months (e.g., cancer)
2. Individuals who are unwilling or unable to wear the ActiGraph device

## **5. Subject Enrollment**

Potential participants will be informed about the study through one of the methods described above (e.g., flyer, provider-including medical interpreters-referral, or via research assistant in the clinic). Participants will complete eligibility screening following any one of the procedures described in section 4. Only after having ample time to review the consent form will the RA

officially guide patients through written informed consent to take part in the research study. Patients who choose to provide their consent will do so electronically (i.e., REDCap eConsent) in the presence of the RA to ensure that all questions or concerns associated with participation are answered. The RA will track participants' preferences with regard to the days and times for intervention delivery and in-person versus Zoom participation. The number of people per group will vary based on participant availability with an expected range between 3 and 10 participants. Once a group is formed and no more than 2 weeks before the first group visit, the RA will schedule an in person visit to conduct informed consent and baseline assessments (see section 6). At this visit patients will receive an ActiGraph watch to wear for 7-10 days, and instructions on how to wear it.

All participants must be capable of understanding the nature of this study as well as the risks and potential benefits. All potential participants will have ample time and opportunity to ask questions or clarify concerns in person (if screened with research assistant) or over email or phone (if screened remotely over REDCap).

All stages of the study will be detailed, including the risks and benefits of the study. No information will be withheld from prospective or active participants regarding the study design. The participant will be reminded that they may decline to participate in this study, and they may discontinue study participation at any time. In this case, a participant will be asked their reason(s) for discontinuation, which may provide valuable feedback for improving future recruitment, retention, or study procedures.

## 6. STUDY PROCEDURES

Once group times have been set, the RA will meet with participants individually over the phone to schedule a visit to review and sign informed consent, answer any remaining questions, complete the baseline assessments, and distribute program manuals. The RA will supervise the participants as they complete all baseline assessments, providing assistance when needed. Additionally, these participants will receive the program manual and an ActiGraph device to wear for the next 7-10 days with instructions on how to use it. Only participants who have consented and enrolled in the study will complete the baseline assessment. Assessments include sociodemographic surveys (e.g., age, race, ethnicity, etc.), clinical information surveys (pain diagnoses, duration, concurrent medical and psychological treatment, narcotic intake), self-report psychosocial measures (physical function, cognitive function, pain intensity, depression, anxiety, coping, pain catastrophizing, mindfulness, fear of pain, gratitude, compassion), and performance based physical function measurements (e.g., 6-minute walk test) and objective physical function, (activity level over 7-day period via ActiGraph). See Table 2 for a full list of study measures. Following the completion of the baseline questionnaires, participants will be provided with and directed to wear an ActiGraph watch which will measure their activity over the next 7-days. After 7-days of valid wear time, participants will return their ActiGraph in their first group session (for in person visits) or mail it in a pre-paid envelope (for zoom visits). Additionally, prior to their first session, all participants will receive a program manual and access to a web platform to support skill practice.

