**Table 2. Aim 2 Open Pilot Measures**

Domain	Measurement Tool and Schedule
Demographic	Age/birth date; gender; biological sex; race/ethnicity; education level; employment status; marital status; household income; disability status; language fluency; people and/or children in the household; RUCA code (i.e., zip code); country of birth; country lived in prior to age 12; years lived in the US, parents' countries of origin; ethnic identity; languages spoken at home; assessment of English fluency. Pre
Clinical	
Type of pain; pain location and number; pain treatments; pain medications; cannabis use for pain; medical comorbidities; mental health conditions and medications. Pre and post, when applicable (chart review and self-report: pain, medication, and medical history questionnaire)
 
Tobacco, Alcohol, Prescription medications, and other Substance (TAPS); assess substance use behaviors. Pre, post

Other	
The Everyday Discrimination Scale – Short (EDS-S); assesses experiences of daily discrimination against minority populations. Pre, post
 
PROMIS Sleep Disturbance – Short Form 6a v1.0; assesses duration and quality of sleep. Pre, post
 
The Pittsburgh Sleep Quality Index (PSQI); assesses sleep quality. Using single item from this scale to assess sleep duration. Pre, post
 
Quota-based pacing questionnaire – assesses ability to engage in meaningful activities and increase activity level gradually. Weekly

Multimodal physical function	
PROMIS Physical Function – Short Form 6b v2.0; assesses one's ability to carry out activities that require physical actions, ranging from self-care to social and work. Pre, post
 
ActiGraph GT3X-BT; watch with blank screen that assesses average step count. Pre, post
 
Six-minute walk test (6MWT) – assesses distance walked in 6 minutes. Pre, post

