The *GetActive* + program used in the open pilot, will incorporate mind-body skills, cognitive behavioral and physical restoration skills (e.g., quota-based pacing) to help individuals increase self-reported, performance based and objective (step count) physical function. This program will teach participants four core skills: 1) weekly goal setting for gradual increase in time spent walking paired with activities of daily living that are meaningful and important to participants (i.e. walk instead of drive to the store; walk to the park with kids) 2) quota-based pacing (increasing walking goal gradually non-contingent of pain); 3) mind-body skills (e.g., diaphragmatic breathing to manage intense pain flares and pain anxiety; body scan to increase body awareness and reduce reactivity to pain sensations; mindfulness exercises to understand the transience of pain and change one's relationship with it; self-compassion when falling short of set goals); and 4) understanding the disability spiral (e.g. how reducing activity perpetuates pain and disability), correcting myths about pain or automatic pain-related thoughts that interfere with meeting program goals. Throughout the 10-week program, participants will be encouraged to increase their time spent walking each week. As in prior mind-body and activity studies, the RA will determine a new walking goal weekly based on whether the open pilot participant met their walking goal in the prior week. Each week participants will increase their activity goal by 10%-20% if they met their prior goal, maintain the same goal if they did not meet it, or decrease the goal by 10%-20% if they did not meet their goal for 2 consecutive weeks. Any risks due to walking will be controlled and monitored by the clinician during the first 20 minutes of each session. The clinician will do so by discussing with each participant how walking went in the week prior, troubleshooting any barriers to walking safely, and coming up with an individualized walking plan for the coming week. Participants will have the opportunity to provide informal feedback on the manual and content throughout the study.

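### The program manual is handed over with the baseline ActiGraph, so the only comparator for the step-count test is recorded after intervention material is supplied

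*Combined protocol and SAP*

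**What the plan says.** Section 6 places the manual at the baseline visit twice. The visit is arranged to obtain consent, to "complete the baseline assessments, and distribute program manuals", and a few lines later "these participants will receive the program manual and an ActiGraph device to wear for the next 7-10 days". A third sentence in the same section says that "prior to their first session, all participants will receive a program manual and access to a web platform to support skill practice". That sentence fits handover at the baseline visit, and it holds neither the manual nor the web platform back until wear has ended.

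On device timing, Section 5 schedules the baseline visit as follows: "Once a group is formed and no more than 2 weeks before the first group visit". Section 6 adds: "After 7-days of valid wear time, participants will return their ActiGraph in their first group session (for in person visits) or mail it", the mailing route being for Zoom participants. Table 2 describes the ActiGraph as a "watch with blank screen that assesses average step count" and schedules it pre and post only.

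On the program, the first core skill listed in Section 6 is "weekly goal setting for gradual increase in time spent walking paired with activities of daily living". Section 6 names ActiGraph activity among the preliminary effectiveness outcomes. Section 9 analyses such outcomes with a paired t-test or Wilcoxon signed rank test in a single arm.

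**The concern.** A baseline should be measured before participants receive any part of the intervention that could move it. Here the intervention aims to raise walking, the outcome is walking, and the written materials are in participants' hands on every baseline wear day. If some participants read the manual or use the web platform early and begin to walk more, the baseline rises and the pre-post gain shrinks.

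There is no control arm and no other step-count measurement, so the data could not separate this from a weaker program effect. What is at stake is the reading of the one objective physical-function outcome in a pilot that looks for signals of improvement and will be used to prepare the next project phase.

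**Working it through.** The plan states no power, alpha or expected effect for step count, so there is no figure of its own to reproduce. The check is mainly one of sequence.

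1. **When material is supplied.** The manual is given at the baseline visit (Section 6, two sentences). Web access comes at an unspecified time before session 1 (Section 6, third sentence).
2. **When steps are recorded.** Over the days after that visit (Section 6). Baseline wear days before the manual is supplied: 0.
3. **Whether anything delays exposure.** Sections 3 and 5 mention only the watch at this visit, which does not contradict Section 6. No section asks participants to leave the manual unopened or postpones its release.
4. **Whether another comparator exists.** No. The trial has one arm (Section 3), measurement is pre and post only (Table 2), and the test is paired (Section 9).
5. **Which outcomes are exposed.** The questionnaires and 6-minute walk test belong to the baseline visit, and the watch is provided after the questionnaires. Of the three physical-function measures, only step count accrues over the following days.
6. **Direction.** Let *b* be any mean rise in baseline steps caused by early material. Observed change = true change − *b*. With *b* > 0 the gain is understated. The documents give no value for *b*.
7. **Illustration of sensitivity only.** Completers: 50 × (1 − 0.20) = 40, from the maximum sample in Section 3 and the attrition estimate in Section 6. Assumed: two-sided alpha 0.05; true d = 0.5 (the medium anchor in Section 9); standard deviation of change unaffected; a share *f* of the effect already present at baseline. Observed d = 0.5 × (1 − *f*). Power is from the noncentral t distribution with 39 degrees of freedom and noncentrality d × √40.

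| Assumed *f* | Observed d | Power |
|---|---|---|
| 0% | 0.50 | 0.87 |
| 10% | 0.45 | 0.79 |
| 20% | 0.40 | 0.69 |
| 30% | 0.35 | 0.58 |
| 50% | 0.25 | 0.34 |

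The values of *f* are assumptions. The table shows what a given share would do, not what share to expect.

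8. **Wear running past session 1.** Section 5 sets a maximum gap but no minimum. For in-person participants, returning the device at session 1 after 7 valid days already implies a gap of about 7 days. For Zoom participants no mailing deadline is given, so the text leaves the point open. The pre label in Table 2, and the later statement in Section 6 that devices come back after the baseline assessment period, indicate that wear is meant to end first.

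**The case against.** The strongest reply is that the documented drivers of walking are not in the manual alone. Section 6 has the research assistant set each new weekly goal from the previous week's result, and the clinician's part in each session includes "coming up with an individualized walking plan for the coming week". Table 3 lists quota-based pacing from session 2. Section 3 places the text reminders within the ten program weeks; Section 6 is looser on their duration but describes them as between-session contact. The blank screen gives participants no step feedback. Step count is a preliminary outcome in a study built for feasibility, and the likely direction would not create a false signal of benefit. Consent already tells participants what the program involves, so withholding the manual cannot produce a fully naive baseline.

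All of this stands, and it limits the weight of the point. It does not alter the sequence in Section 6 or explain why the material must be supplied before wear ends.

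Two stronger readings are tempting. A reader might infer that baseline steps are in fact contaminated. The documents do not support that: they do not describe the manual's content or show that anyone uses it before session 1. A reader might also infer that baseline wear routinely runs into the program, and might try to count the days affected. In-person return at session 1 argues against this. The remaining Zoom ambiguity is minor, and because a valid wear day is not defined, such counts would be firmer than the text allows.

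**Conclusion.** The point holds as a possible and avoidable bias in one secondary outcome. As written, the baseline step count is recorded entirely after the manual is supplied, and possibly after web access is opened. The size is unknown. The most likely direction is an understated gain, on the assumption that early material, if used, increases walking. The feasibility, acceptability and fidelity benchmarks are untouched, and the baseline questionnaires and 6-minute walk test are largely outside it. The wear-timing question is a small companion issue confined to Zoom participants. This is a low-cost improvement worth making, not a defect that threatens the study's main purpose.

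**What to change.** - **Section 6, main change.** Remove the manual from the two baseline-visit sentences. Release the manual and web access only once baseline wear is complete: at device return in session 1 for in-person participants; by link, with mailing as back-up, after wear ends and just before session 1 for Zoom participants. Reword the sentence on supply before the first session to match.
- **Section 5, minor companion change.** Schedule the baseline visit early enough within the existing 2-week window for wear to end before session 1 for Zoom participants too.
- **Section 9, minor companion change.** State that baseline mean steps use only valid days before session 1.

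Costs: one link or mailing per Zoom participant, a small risk that a mailed manual arrives late, and somewhat tighter Zoom scheduling. Some participants may have fewer usable baseline days, because days after session 1 would not count. In-person participants need no extra contact, since they already return the device at session 1. The change removes only part of any anticipatory effect, because consent already describes the program. For anyone whose baseline wear is already recorded under the present wording, the exposure cannot be undone and should be reported as a limitation.

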All participants will wear ActiGraph devices to monitor activity levels for 7-10 days after their baseline assessment and post-intervention assessment. Following the baseline assessment period, participants will return the ActiGraph device either in person at their first group session or mail the device back to study staff if they will be attending group sessions virtually. The post-intervention assessments will be scheduled to take place approximately 3 days after the last group session (e.g., Session 10). Participants will receive their ActiGraph device and wear it for the following 7-10 days. Participants will return their ActiGraphs via pre-paid envelopes provided by study staff. Participants will also be given the option to share contact information with the other group members following the post-program assessments. This is an optional procedure for those interested in staying in touch following group sessions.

Only trained study staff will have access to the data collected at baseline and post-program. Participants' data will be identified by an ID number only, and a link between names and ID numbers will be password-protected and kept separately. The information on the ActiGraph accounts will be password protected and only the study staff and patient will have access to that information. Training sessions will be audio-recorded and reviewed to ensure fidelity. All group sessions will be audio-recorded. Recordings will be used for weekly clinical supervision (e.g., problem solve challenging cases), and to assess study therapist's competency and fidelity to the content of each session. All study staff will have up to date Collaborative Institutional Training Initiative (CITI) certifications. All study procedures will be conducted using our published methodology.

Following the conclusion of the program, patients will have the option to participate in an exit interview. These interviews will be conducted utilizing procedures outlined by Krueger and guided by a semi-structured IRB approved interview guide. The goal of these interviews will be to understand the experiences of participants and garner feedback on the program. This feedback will eventually be used to further optimize the *GetActive+* program for use in future studies. Participants will be able to choose whether they would like to attend the exit interview in person

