Participants will be compensated \$60 for completing the baseline visit and up to \$100 for the 7–10-day baseline ActiGraph assessment (e.g., \$10 per day up to 7-days; additional \$30 for 7 days of complete and valid data). Participants will also receive up to \$150 worth of travel compensation (e.g., if sessions are in person, \$15 per session for 10 sessions). If participants attend group sessions virtually, they will not be subject to the compensation associated with transportation. To incentivize long-term engagement with the program, participants will receive a \$50 bonus for attending at least 8 of the 10 sessions. Participants will also receive \$100 for the completion of the post-program assessments and up to \$155 for the post-program ActiGraph data collection period (e.g., \$15 per day up to 7-days; additional \$50 provided for 7 days of complete and valid data). In addition to all the above, participants will be given the opportunity to earn \$40 for attending an in-person post-program exit interview (\$25 for remote exit interviews). Select participants (based on randomization and interest) can also receive \$40 for an additional focus group. Payments will be submitted and sent to participants following each major time point (i.e., baseline, final group session, and post-program exit interview). Overall, participants of the open pilot will earn up to \$695.

All study procedures for Spanish speaking groups will be identical to English groups. Participant interactions will be in Spanish through a native Spanish speaking RA and group facilitator (i.e., a native Spanish-speaking social worker). Spanish speaking study staff will be fully trained in the

GetActive+ intervention and study procedures. All study materials are translated and spot check by a Spanish speaking RA.

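### Could days after the program starts enter the baseline ActiGraph step count, since no minimum lead or cut-off is written?

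*Combined protocol and SAP*

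**What the plan says.** - **Lead time.** Section 5 (Subject Enrollment) places the consent and baseline visit "no more than 2 weeks before the first group visit". This is the only limit on the interval, and it is an upper one.
- **Wear.** Section 6, first paragraph, says "these participants will receive the program manual and an ActiGraph device to wear for the next 7-10 days". Later in the same paragraph participants are "directed to wear an ActiGraph watch which will measure their activity over the next 7-days".
- **Return.** After seven days of valid wear, participants "return their ActiGraph in their first group session (for in person visits) or mail it in a pre-paid envelope (for zoom visits". The paragraph after Table 3 repeats the rule: "Following the baseline assessment period, participants will return the ActiGraph device either in person at their first group session or mail the device back".
- **Payment.** The compensation paragraph of Section 6 pays $10 a day for at most seven baseline days, plus $30 "for 7 days of complete and valid data".
- **Materials.** The manual is handed over with the device at the baseline visit. A later sentence says that "prior to their first session, all participants will receive a program manual and access to a web platform to support skill practice".
- **Analysis.** Table 2 lists the ActiGraph at the pre and post time points. Section 9 compares pre with post by a paired t-test or the Wilcoxon signed rank test, and does not say which wear days make up the baseline value.

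**The concern.** This is a single-arm pilot, so the change in step count is only as sound as its baseline. The program aims to raise walking. Section 6 has the clinician spend the first 20 minutes of each session on walking, including "coming up with an individualized walking plan for the coming week". A day recorded after session 1 is therefore a day under treatment.

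For in-person participants, handing the device back at session 1 ends the recording; a short lead costs them baseline days or delays the return. For Zoom participants nothing in the text stops the recording at session 1. Someone booked a few days beforehand, or someone with invalid days to make up, could go on wearing the watch into the program. If walking rose early, the baseline would be too high and the measured improvement too small, and this would happen in the remote format only.

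Three smaller points appear to add to this: two descriptions of the wear length, a payment that might encourage extra wear, and two sentences on when the manual arrives.

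**Working it through.** **1. What length of record is intended?** The plan's own payment figure answers this. Seven days at $10 plus the $30 bonus is 7 × 10 + 30 = $100, the stated baseline maximum. Nothing is paid beyond seven days, and no sentence asks for ten valid days. The two wear statements fit one reading: a span of 7 to 10 days in which to obtain seven valid days.

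**2. How many days could fall on or after session 1?** Let L be the lead in days from baseline visit to session 1, and W the number of wear days.

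- Visit day counted as a wear day: overlap = max(0, W − L).
- Visit day not counted: overlap = max(0, W + 1 − L).

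| Lead L | W = 7, visit day counted | W = 7, visit day not counted |
|---|---|---|
| 8 to 14 | 0 | 0 |
| 7 | 0 | 1 |
| 6 | 1 | 2 |
| 5 | 2 | 3 |
| 3 | 4 | 5 |

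For a full ten-day span with the visit day counted, overlap is 0 at leads of 10 to 14 and 10 − 7 = 3 days at a lead of 7. So leads of 7 or 8 days upward clear a seven-day record, and they lie inside the 14-day cap. At a lead of 7 with the visit day not counted, the single overlapping day is the day of session 1 itself, part of which precedes the session.

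**3. What could overlap do to the result?** The documents give no expected step change and no early uplift, so both are assumed here. Suppose a true rise of 20%, with steps on d of 7 baseline days higher by a fraction h. Then

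observed change = 1.20 / (1 + (d/7) × h) − 1.

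| h | d = 1 | d = 2 | d = 3 |
|---|---|---|---|
| 0 | 20.0% | 20.0% | 20.0% |
| 0.05 | 19.1% | 18.3% | 17.5% |
| 0.10 | 18.3% | 16.7% | 15.1% |

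A harsher case is a 3-day lead with the visit day counted, which puts 4 of 7 days after the start. If those days already show 10% to 50% of the final change (assumed), the measured change shrinks by 0.571 × 0.10 = 5.7% to 0.571 × 0.50 = 28.6% of its value. Zero remains plausible for the days just after session 1, because Table 3 lists only deep breathing for that session, although the narrative describes a walking plan at every session.

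**4. Which days does the text intend?** Three statements point the same way.

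- Table 2 calls the measurement pre and post; a day after session 1 is not a pre day.
- The in-person rule puts seven valid days first and the return at session 1 second, which implies a lead of about a week.
- The paragraph after Table 3 refers to the wear as a baseline period that ends before the device goes back, and speaks of remote sessions as still to come.

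No sentence tells anyone to count program days as baseline. Payment by the day implies that wear is tracked by the day, so pre-session days should be identifiable at analysis.

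**5. Manual timing.** The baseline visit comes before session 1. A manual given at that visit has been given before the first session, so both sentences are true. The manual is not in the documents, and nothing in them shows that holding it changes step count.

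**The case for a change.** The strongest contrary case is that intention is not a rule. A 3-day lead satisfies Section 5 as well as a 12-day lead does, and a remote participant short of seven valid days is paid to continue. Section 2 says the pilot is meant to improve study procedures for later trials, so a loose baseline definition is worth tightening while that costs only a sentence. Because the possible bias affects only mailed devices, it could also make remote and in-person participants look different for no real reason.

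Part of this stands. There is no written minimum lead and no written cut-off for mailed devices, and either would be easy to state. The payment argument is weaker than it looks, since daily pay stops at seven days and the incentive acts only on someone who has not yet reached seven. The argument for a lead of ten days or more, to allow spare days for invalid wear, needs a daily validity rate that the documents do not give.

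Actual harm needs several things together: Zoom attendance, a short lead or invalid days, an early rise in steps, and an analyst who labels post-session days as pre. The last of these runs against Table 2.

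**Conclusion.** The plan leaves a detail unwritten that staff and analysts would fill sensibly: baseline step count comes from valid wear days before session 1, and the visit is booked about a week or more ahead. The wear-length, payment and manual points are not inconsistencies once the sentences are read together.

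The possible effect is confined to one preliminary effectiveness outcome, in an analysis that Section 9 says was not powered for specific effects. It would bias the change toward zero and would not create a false signal, provided walking does not fall after session 1. Its size cannot be found from the documents and may be nil; the percentages above rest wholly on assumed uplifts and an assumed true rise. The feasibility, acceptability and fidelity benchmarks in Table 4 do not use step count and are unaffected. No change to the plan is called for.
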